4.1 Primary Objective

- 1. Reduction of MaSC in DCIS, LCIS, ALH or ADH in patients receiving rapamycin
- 2. Reduction of malignant markers in DCIS, LCIS, ALH or ADH in patients receiving rapamycin

4.2 Secondary Objectives

- 1. Toxicity
- 2. Surgical complications

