6. TREATMENT PLAN

This is a phase II window of opportunity trial in which women with a diagnosis of DCIS, LCIS, ALH or ADH will be treated with rapamycin at 2 mg/day for 5-7 days. Surgery will be performed 3-7 days after the last dose of rapamycin. An evaluable patient for toxicity is any patient who has received at least 1 dose of rapamycin. An evaluable patient for efficacy is any patient who has completed at least 5 days of rapamycin therapy and has had surgery within the 7-day window.

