11. DURATION OF THERAPY

Treatment duration is 5-7 days

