12. FOLLOW-UP POST-THERAPY

Patients will be followed 3 months after surgery at the time of routine clinic visit or via phone call with study personnel, See APPENDIX 3 –subsection titled Research Chart (case report form needed for data collection during this 3-month follow-up visit).

Treatment after study completion will be left to the discretion of the treating physician(s) and will not be considered part of this study. However, patients should still be followed for surgical complications as part of their standard of care.

Procedures	Screening & Baseline	Day 1-7 ⁴	Day before Surgery	Surgery ²	3 month Follow-Up
Tissue procurement ¹				Х	
Informed consent	х				
Rapamycin administration		Х			
Cancer history ³	х		х		
Physical exam ³	х		х		
CBC w/ diff	X ³		Х		
Comprehensive metabolic panel	X ³		х		
Lipid panel	х		х		
Estradiol ⁵	Х		х		
FSH⁵	Х		х		
Toxicity (AE) assessment			Х		Х

13. SCHEDULE OF EVENTS

¹ Fresh tissue procurement will be required for study purposes.

² Surgery can take place 3-7 days after completion of rapamycin treatment

- ³ Pre-study laboratory tests, cancer history, and physical exam (including review of systems) must be completed within 28 days prior to registration. At the discretion of the treating physician and only if clinically indicated as part of their standard of care, the pre-study CBC and CMP will be repeated one (1) day prior to treatment administration.
- ⁴ Rapamycin will be administered for 5-7 days
- ⁵ Estradiol and FSH are required only if patient is under 60 years of age and has not had a bilateral oophorectomy.

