Baseline adverse events and serious adverse events will be captured using the UT Health San Antonio Mays Cancer Center Master Adverse Events Document (or proper AE tracking mechanism as per Clinical Trial Office policy) for each patient using CTCAE V. 4.03 for the grading and attribution of adverse events (*Appendix 1*).

Usage of the UT Health San Antonio Mays Cancer Center Master Adverse Events Document (or proper AE tracking mechanism as per Clinical Trial Office policy) centrally documents:

- 1. the event and grades the seriousness of the event,
- 2. if the event was a change from baseline,
- 3. the determination of the relationship between the event and study intervention,
- 4. if the event was part of the normal disease process, and

5. What actions were taken as a result of the event.

c. Safety Definitions

For this study, the following safety definitions will be applicable:

Adverse Event Definition: An adverse event (AE) is defined as any untoward or unfavorable medical occurrence in a human subject, including any abnormal sign (for example, abnormal physical exam or laboratory finding), symptom, or disease, temporally associated with the subject's participation in the research, whether or not considered related to the subject's participation in the research. For this study, all adverse events will be documented starting with day 7 and ending 30 days after the last dose of study drug is received.

Serious Adverse Event Definition: A serious adverse event (SAE) is defined as any adverse event that:

- 1. results in death;
- 2. is life-threatening (places the subject at immediate risk of death from the event as it occurred);
- 3. results in inpatient hospitalization or prolongation of existing hospitalization;
- 4. results in a persistent or significant disability/incapacity;
- 5. results in a congenital anomaly/birth defect; or
- 6. based upon appropriate medical judgment, may jeopardize the subject's health and may require medical or surgical intervention to prevent one of the other outcomes listed in this definition

Unanticipated Problems Involving Risks to Subjects or Others Definition: Unanticipated problem involving risk to subjects or others includes any incident, experience or outcome that meets all of the following criteria:

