APPENDIX 3 – Data Collection & Submission

Study-specific instructions regarding the entry and submission of data using paper CRFs or eCRFs using an electronic data system (e.g. REDCap), will be provided at the time of training prior to study activation. UT Health San Antonio Mays Cancer Center compliance policies of the Cancer Therapy & Research Center at the UT Health San Antonio DSMP regarding data collection and submission will be strictly enforced.

a. Research Chart

In addition to the regular hospital chart, a separate patient research folder will be kept which includes the patient's signed, dated informed consent document.

Case Report Forms to be submitted within 5 days of patient's first dose of study treatment:

• Master Adverse Event Form (or proper AE tracking mechanism as per Clinical Trial Office policy): Update to reflect the adverse events that are present at baseline.

Case Report Forms to be submitted no later than 1 week after End of Treatment Visit:

• Master Adverse Events Form (or proper AE tracking mechanism as per Clinical Trial Office policy): All AEs should be finalized within 30 days of last dose

Case Report Forms to be completed during follow-up:

• Master Adverse Events Form (or proper AE tracking mechanism as per Clinical Trial Office policy): *Reflecting 3-month toxicity status*

Category	Drug Name
Strong CYP3A Inhibitors	 Boceprevir, Clarithromycin, Cobicistat, Conivaptan, Danoprevir, Grapefruit juice (citrus paradisi fruit juice, 240 mL TID), Elvitegravir, Idealisib, Indinavir, Itraconazole, Ketoconazole, LCL161, Lopinavir, Mibefradil, Nefazodone, Nelfinavir, Posaconazole, Ritonavir, Saquinavir, Telaprevir, Telithromycin, Tipranavir, Troleandomycin, Voriconazole
Strong CYP3A Inducers	Avasimibe1,2, Carbamazepine, Enzalutamide, Mitotane, Phenobarbital, Phenytoin, Rifabutin, Rifampin (Rifampicin)2, St. John's wort (hypericum perforatum)2

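### Appendix 2 stops adverse-event documentation on post-operative day 23-27, other sections collect it at 3 months, and surgical complications, a secondary objective, have no ascertainment window of their own

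*Combined protocol and SAP*

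**What the plan says.** Section 4.2 lists two secondary objectives: toxicity and "Surgical complications". Section 6 fixes the timing of the operation: "Surgery will be performed 3-7 days after the last dose of rapamycin".

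Two statements place the end of adverse-event recording at 30 days:

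- Appendix 2, part c: recording of every adverse event begins on day 7, "ending 30 days after the last dose of study drug is received".
- Appendix 3, part a, under the forms due after the End of Treatment Visit: "All AEs should be finalized within 30 days of last dose".

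Four statements look beyond 30 days:

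- The schedule of events (Section 13) marks the toxicity assessment twice. By column order the marks fall on the day before surgery and at the 3-month follow-up.
- Section 12 describes a 3-month contact, in clinic or by phone, and refers to a case report form for it.
- Appendix 3 requires the Master Adverse Events Form again during follow-up: "Reflecting 3-month toxicity status".
- Section 16.6 sends routine events, including unrelated ones, to the eCRF at the intervals of the schedule.

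No section defines surgical complications, gives them a form of their own, or states the period over which they are ascertained. Section 15.2 contains no analysis of them.

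**The concern.** The Appendix 2 window is anchored to the last dose, whereas the objective concerns what happens after the operation. Because the operation comes later, part of the 30 days has passed before any surgical complication can occur. The schedule has no adverse-event assessment at surgery or between surgery and month 3. The 3-month form is described by toxicity status; it does not name surgical complications or ask for dates of events in the interval.

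Section 14 describes the drug as immunosuppressive, and Section 14.2.1 reports a dose-related surgical complication in renal transplant patients, so complications are a natural thing to count here. If staff close the log under Appendix 2, they count one set of events; if they follow the schedule, they may count another. The resulting proportion has no single defined period, and in a small trial a few events can move it visibly.

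**Working it through.** The plan states no post-operative coverage figure, so there is none to reproduce. The check is day arithmetic, then a comparison of sections.

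**Inputs.** Dosing lasts 5-7 days (Section 11: "Treatment duration is 5-7 days"). The interval from last dose to surgery is 3-7 days (Section 6). The window ends 30 days after the last dose (Appendix 2). The follow-up contact is 3 months after surgery (Section 12), taken here as 90-92 days, which is an assumption.

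**Post-operative days inside the window** = 30 minus the interval from last dose to surgery.

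- Interval 7 days: 30 - 7 = 23.
- Interval 3 days: 30 - 3 = 27.

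The length of dosing cancels out. Counting from the first dose:

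| Last dose | Surgery | Window closes | Post-operative days covered |
|---|---|---|---|
| Day 5 | Day 8-12 | Day 35 | 27-23 |
| Day 6 | Day 9-13 | Day 36 | 27-23 |
| Day 7 | Day 10-14 | Day 37 | 27-23 |

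The day 7 start in the same sentence does not shorten post-operative coverage, because the earliest surgery is day 8. It does leave out earlier dosing days, which is a separate matter.

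**From window closure to the 3-month contact**

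- Shortest: 90 - 27 = 63 days.
- Longest: 92 - 23 = 69 days.

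**Which late events other sections catch**

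- Serious events: Section 16.1.3 covers those during the study or within 30 days of the last dose, whatever the attribution. A late serious complication is reportable if the study is taken to include the 3-month follow-up.
- Events at least possibly attributed to the drug: Section 16.2 requires reporting after 30 days.
- Events already identified: Section 16 follows them to resolution, another explanation or death.
- Events still present at 3 months: the scheduled assessment and form should capture them.

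What remains is a complication that is non-serious, not attributed to the drug, begins after post-operative day 23-27, and has resolved by month 3. Under Section 16.6 and the schedule it could be entered at the 3-month contact if it is asked about and recalled. Under Appendix 2 it need not be entered.

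**What one event is worth.** Section 15.2 gives a group size of 24 or more and expects 50-60 recruits. One unrecorded complication changes the proportion by 1/24 = 4.2 percentage points, 1/50 = 2.0, or 1/60 = 1.7.

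**The case against.** The best defence is that 3-month collection is already planned. The schedule marks it, Section 12 refers to a form for it, and Appendix 3 names that form. The Master Adverse Events Form is updated from baseline onward and records events, relationship and actions taken, so it may work as a running log and the 3-month entry may include interval events. The 30-day finalisation line in Appendix 3 sits with the end-of-treatment submission and can be read as the deadline for that submission alone. Sections 16, 16.1.3 and 16.2 narrow the gap further.

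Most of this stands. It rules out three stronger readings that a reader might infer:

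- That adverse events are collected only to 30 days and all later complications are lost. The 3-month assessment and form contradict this.
- That the complication rate will certainly be too low, or that the uncovered calendar time measures the loss. The documents give no incidence or timing of complications, and a share of days is not a share of events.
- That Section 12 hands in-study complications to routine care. The sentence "patients should still be followed for surgical complications as part of their standard of care" follows one about treatment after study completion and does not withdraw the 3-month study contact.

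The defence does not remove the Appendix 2 sentence, which applies to all adverse events in this study. Nor does it supply a period for surgical complications. Section 16.2 filters on attribution to the drug, while the objective covers surgical complications whatever their cause.

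**Conclusion.** The point holds as an internal inconsistency that bears on a secondary objective. Appendix 2 closes documentation on post-operative day 23-27, while the schedule, Section 12, Section 16.6 and the Appendix 3 follow-up form carry it to 3 months, 63-69 days later. The 23-27 days follow directly from the stated intervals; the 63-69 days rest on taking 3 months as 90-92 days.

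The exposed events are mainly non-serious complications, not attributed to the drug, that start after the window and resolve before the 3-month contact. They may go unrecorded, so the reported rate could be too low and could depend on the section followed. The number of such events cannot be estimated from the documents. Two readings remain open: whether the study in Section 16.1.3 includes the follow-up period, and whether the 3-month form covers the interval or only the status on that day. The text should settle both.

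**What to change.** Reconcile Appendix 2 (part c), Appendix 3 (part a), Section 12 and the schedule of events so that they state one period for surgical complications: from surgery to the 3-month contact, regardless of attribution to the drug. Record each complication on the existing Master Adverse Events Form with onset and resolution dates, and make clear that the 3-month entry covers the whole interval. Report the proportion of patients with a complication over that single period.

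The cost is a text amendment and a few more event entries. Complications that began and ended between visits will rest partly on recall at the 3-month contact, which is a limitation to acknowledge. No new visit or form is needed.

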APPENDIX 3 – Data Collection & Submission

Study-specific instructions regarding the entry and submission of data using paper CRFs or eCRFs using an electronic data system (e.g. REDCap), will be provided at the time of training prior to study activation. UT Health San Antonio Mays Cancer Center compliance policies of the Cancer Therapy & Research Center at the UT Health San Antonio DSMP regarding data collection and submission will be strictly enforced.

a. Research Chart

In addition to the regular hospital chart, a separate patient research folder will be kept which includes the patient's signed, dated informed consent document.

Case Report Forms to be submitted within 5 days of patient's first dose of study treatment:

• Master Adverse Event Form (or proper AE tracking mechanism as per Clinical Trial Office policy): Update to reflect the adverse events that are present at baseline.

Case Report Forms to be submitted no later than 1 week after End of Treatment Visit:

• Master Adverse Events Form (or proper AE tracking mechanism as per Clinical Trial Office policy): All AEs should be finalized within 30 days of last dose

Case Report Forms to be completed during follow-up:

• Master Adverse Events Form (or proper AE tracking mechanism as per Clinical Trial Office policy): *Reflecting 3-month toxicity status*

Category	Drug Name
Strong CYP3A Inhibitors	 Boceprevir, Clarithromycin, Cobicistat, Conivaptan, Danoprevir, Grapefruit juice (citrus paradisi fruit juice, 240 mL TID), Elvitegravir, Idealisib, Indinavir, Itraconazole, Ketoconazole, LCL161, Lopinavir, Mibefradil, Nefazodone, Nelfinavir, Posaconazole, Ritonavir, Saquinavir, Telaprevir, Telithromycin, Tipranavir, Troleandomycin, Voriconazole
Strong CYP3A Inducers	Avasimibe1,2, Carbamazepine, Enzalutamide, Mitotane, Phenobarbital, Phenytoin, Rifabutin, Rifampin (Rifampicin)2, St. John's wort (hypericum perforatum)2

